1.2 SCHEMATIC OF STUDY DESIGN

An overview of the study design is provided in [Figure 1](#).

Figure 1 Overview of Study Design

1.3 SCHEDULE OF ACTIVITIES

The schedule of the activities is provided in [Table 1](#) to [Table 3](#).

Table 1 Schedule of Activities – Main Table

Day	Screening up to Day-28	Treatment Period 1 & Washout period of 9 Days ± 1 Day up maximum of 18 Days								Treatment Period 2														Follow-up Visit (15 to 20 days after last itraconazole)			
		Day -1	Day 1	Day 2	Day 3	Day 4	Day 5	Day 6	Day 8	Day -1	Day 1	Day 2	Day 3	Day 4	Day 5	Day 6	Day 7	Day 8	Day 9	Day 10	Day 11	Day 12	Day 13	Day 14	Day 15	Day 16	
Assessments																											
Informed Consent	x																										
Demography	x																										
Medical History	x																										
Physical Examination^a	x	x								x													x				x
In house Period		x	x	x	x	x					x	x	x	x	x	x	x	x	x	x	x	x	x	x			
Discharge from the unit							x																x				
Ambulatory Visit								x	x	x														x	x	x	x
Vital Signs^b	x	x	x	x	x	x	x	x	x	x	x	x	x	x	x	x	x	x	x	x	x	x	x	x	x	x	
12-Lead ECG^c	x	x	x	x	x	x	x	x	x	x	x	x	x	x	x	x	x	x	x	x	x	x	x	x	x	x	
Serology	x																										
Pregnancy Test^d	x	x																									
Hormone Panel^e	x	x																									
Alcohol Breath Test	x	x							x																		
Urine Drugs of Abuse	x	x							x																		
Urinalysis	x	x			x				x	x					x		x		x					x	x		
Blood Chemistry	x	x		x						x	x				x		x		x					x	x		
Hematology	x	x		x						x	x				x		x		x					x	x		
Coagulation	x	x																									
RO7017773 Administration^f																											
Itraconazole Administration^g										x	x	x	x	x	x	x	x	x	x	x	x	x	x	x	x		
Standard Meal^h	x	x ⁱ								x	x	x	x	x ⁱ	x	x	x	x	x	x	x	x	x	x	x		
Itraconazole and metabolites PK sample										x					x	x	x	x	x	x	x	x	x	x	x	x	
Clinical Genotyping		x																									
C-SSRS	x	x						x			x			x										x			
Adverse Events	x	x	x	x	x	x	x	x	x	x	x	x	x	x	x	x	x	x	x	x	x	x	x	x	x	x	
Concomitant medications	x	x	x	x	x	x	x	x	x	x	x	x	x	x	x	x	x	x	x	x	x	x	x	x	x	x	

PK = Pharmacokinetic

Table 1 Schedule of Activities – Main Table (cont.)

- a) Physical examination will include body weight at screening and follow-up, and height at screening when body mass index (BMI) will be derived.
- b) Vital signs will include blood pressure, pulse rate, and (at selected time points) body temperature. Vital sign measurements will be taken after the participant has rested in a supine position for at least 5 minutes.
- c) Triplicate 12-lead ECG will be recorded after the participant has rested in a supine position for at least 10 minutes.
- d) Serum test at screening, urine test at Day -1.
- e) Hormonal panel for postmenopausal women only.
- f) The oral dose of RO7017773 will be given in the morning, 30 min after starting a standardized breakfast.
- g) *An oral dose of itraconazole will be given twice daily (2 x 200 mg) with 12 hours between the two doses and under fed conditions, i.e., 30 minutes after starting a meal in the morning and the evening on Day 1 only. On Days 2 to 9, an oral dose of itraconazole will be given once daily (1 x 200 mg) under fed conditions, i.e., 30 minutes after starting a meal in the morning.*
- h) On the morning of study drug treatment, breakfast should be consumed within 30 min or less. On itraconazole administration days, the evening meal should be consumed within 30 min or less.
- i) The same food conditions (in terms of meal constitution and time of administration) will apply on RO7017773 administration days.

Table 2 Schedule of Activities – Detailed Table Period 1

Day		Vital Signs ^a	ECG-12 lead ^c	Safety Laboratory Tests	RO7017773 Administration	Standard Meal		Clinical Genotyping
Day 1		x ^b	x			x ^e		x
					x ^d			
		x ^b	x					
		x	x					
							x	
		x	x					
		x ^b	x					
Day 2		x	x				x	
Day 3		x	x	x				
Day 4		x	x					
Day 5		x	x					
Day 6								
Day 8		x	x	x				

PK = Pharmacokinetic

Table 2 Schedule of Activities – Detailed Table Period 1 (cont.)

- a) Blood pressure and pulse rate will be measured after the participant has rested in a supine position for at least 5 minutes.
- b) Body temperature to be measured.
- c) Triplicate 12-lead ECG will be recorded after the participant has rested in a supine position for at least 10 minutes.
- d) The oral dose of RO7017773 will be given in the morning, 30 min after starting a standardized breakfast.
- e) On the morning of study drug administration, breakfast should be consumed within 30 min or less.

Table 3 Schedule of Activities – Detailed Table Period 2

Day		Vital Signs ^a	ECG-12 lead ^d	Safety Laboratory Tests	Itraconazole Administration ^e	RO7017773 Administration	Standard Meal ^g		Itraconazole & Metabolites PK Sample
Day 1		x ^b	x						x
					x		x		x
					x		x		x
					x		x		x
		x ^{b,c}	x ^c	x	x		x		x ^c
		x ^b	x						x
		x	x						x
							x		x
		x	x						x
		x ^b	x						x
		x	x						x
									x
							x		x
		x ^b	x		x		x		x
							x		x
		x	x		x		x		x
				x	x		x		x
Day 2									
Day 3									
Day 4									
Day 5									
Day 6									
Day 7									
Day 8									
Day 9									
Day 10									
Day 11									
Day 12									
Day 13									
Day 14									
Day 15									
Day 16		x	x	x					x

PK = Pharmacokinetic

Table 3 Schedule of Activities – Detailed Table Period 2 (cont.)

- a) Blood pressure and pulse rate will be measured after the participant has rested in a supine position for at least 5 minutes.
- b) Body temperature to be measured.
- [REDACTED]
- c) Heart rate to be measured.
- d) Triplicate 12-lead ECG will be recorded after the participant has rested in a supine position for at least 10 minutes.
- e) *An oral dose of itraconazole will be given twice daily (2 x 200 mg) with 12 hours between the two doses and under fed conditions, i.e., 30 minutes after starting a meal in the morning and the evening on Day 1 only. On Days 2 to Day 9, an oral dose of itraconazole will be given once daily (1 x 200 mg) under fed conditions, i.e., 30 minutes after starting a meal in the morning.*
- [REDACTED]
- f) Blood samples to be drawn.
- g) On the morning of study drug administration, breakfast should be consumed within 30 min or less. On itraconazole administration days, the evening meal should be consumed within 30 min or less.

2. INTRODUCTION

2.1 STUDY RATIONALE

RO7017773 is being developed for the treatment of the 2 core domains of Autism Spectrum Disorder (ASD): social communication deficits and repetitive and restrictive behaviors. RO7017773 has the potential to normalize GABAergic signaling in key brain regions implicated in ASD without the side effects of non-specific GABA_A modulators (e.g., benzodiazepines).

The aim of the study is to investigate the effect of multiple oral doses of itraconazole on the pharmacokinetics (PK) of RO7017773.

CYP3A inhibitors are likely to increase the plasma exposure of RO7017773. Itraconazole, a potent and widely used triazole antifungal agent, is a strong CYP3A inhibitor and is commonly used as a prototypical CYP3A inhibitor in drug-drug interaction (DDI) studies.

This study will allow assessing the magnitude of increase in systemic exposure of RO7017773 when co-administered with CYP3A inhibitors like itraconazole.

The rationale for the study design is provided in Section 4.2.

[figure not shown]
2.2 BACKGROUND

ASD is a complex, heterogeneous neurodevelopmental disorder characterized by impairments in social communication and interaction, as well as by repetitive behaviors and restricted interests (Diagnostic and Statistical Manual of Mental Disorders [DSM 5]). The estimated prevalence of ASD in the United States is 1 in 68 children ([CDC, 2014](#)), and it is estimated that 1% of the world's population have ASD ([WHO, 2013](#)).

No approved pharmacological treatment exists for the core social communication and social interaction deficits and repetitive behavior of ASD, and this disorder continues to be an area of high unmet medical need. Current treatments for associated symptoms of ASD may include antipsychotics (risperidone and aripiprazole) used for the treatment of irritability associated with ASD symptoms. Multiple lines of evidence suggest that an imbalance between excitatory/inhibitory neurotransmission in favor of excitation may arise from a dysfunction of the GABAergic signaling system (the main inhibitory neurotransmitter system in the brain) early in development; this imbalance represents a central characteristic of the neurobiology of autism, leading to some of the impairments observed in individuals with ASD.

2.2.1 Background on RO7017773

RO7017773 is a selective GABA_A $\alpha 5$ subunit containing receptor positive allosteric modulator.

A high-contrast, black and white image showing a series of horizontal bands. The bands are thick and appear to be composed of multiple layers. The top band is dark, followed by a thin white band, then a thick dark band, and another thin white band. This pattern repeats three more times below, creating a stepped, staircase-like effect. The image is set against a black background.

2.2.1.2 Previous and ongoing clinical studies

At the time of writing, RO7017773 has been investigated in 2 healthy adult participant studies, one ongoing Entry-into-Human study (BP40091) with single ascending doses (SAD) and multiple ascending doses (MAD) and one completed positron emission tomography (PET) study (BP40257).

44

2.2.2 Background on Itraconazole

Itraconazole is a potent and widely used triazole antifungal agent and a prototypic competitive inhibitor of CYP3A ([FDA, 1999; CHMP, 2012; Bjornsson et al 2003]). It reduces the metabolism and increases exposure of drugs metabolized by the CYP3A4 pathway. Itraconazole is available as oral capsules and the recommended doses in adults are 100 or 200 mg once daily (QD) or twice daily (BID) administered with food.

Itraconazole is generally well tolerated. Gastrointestinal disturbances are the most frequently reported AEs following the oral use of itraconazole. Nausea, vomiting, diarrhea, and abdominal pain have been commonly reported in patients undergoing treatment of systemic fungal infections. These AEs are dose-related and may be minimized by giving itraconazole with food. Rash was also observed in patients; however, rash tends to occur more frequently in immunocompromised patients receiving immunosuppressive medications. Itraconazole has been associated with rare cases of serious hepatotoxicity. Some of these cases had neither pre-existing liver disease nor a serious underlying medical condition and some of these cases developed within the first week of treatment. If clinical signs or symptoms develop that are consistent with liver disease, treatment should be discontinued and liver function testing performed. Other AEs include pruritus and angioedema, and rare cases of anaphylaxis have been reported. Fatigue, headache, dizziness, hypertension, decreased libido, impotence, visual disturbances and somnolence may also occur ([SmPC](#)).

A detailed description of the chemistry, pharmacology, efficacy and safety of itraconazole is provided in the Summary of Product Characteristics ([SmPC](#)).

2.3 BENEFIT/RISK ASSESSMENT

This study is being conducted to evaluate the PK of RO7017773 with and without concomitant administration of itraconazole to investigate the effects of inhibition of CYP3A on RO7017773 exposure.

In order to minimize the number of participants required in the study, a within-subject study design has been chosen and an open-label, one-sequence design was selected.

Itraconazole is generally well tolerated. The itraconazole dosing regimen in this study is consistent with the prescribing recommendations for itraconazole ([SmPC](#)). Approved dosing regimens for the treatment of fungal infections include doses up to 200 mg BID

for periods of up to one year. Itraconazole doses of 200 mg QD or BID are also commonly used in DDI studies to ensure adequate CYP3A inhibition (Ke et al 2014; Liu et al 2015).

There is extensive clinical experience of the use of itraconazole and the potential clinical risks are well characterized. While some side effects occur frequently (e.g., headache, abdominal pain, and nausea), these generally do not require any medical intervention and side effects requiring treatment tend to occur rarely. There are a number of contraindications and precautions within the approved itraconazole prescribing information, but potential risks will be minimized by enrolling only healthy participants and specifically excluding people for whom the drug is contraindicated (e.g. history of heart failure).

Itraconazole PK will be measured when given alone and concomitantly with RO7017773 to ascertain that the PK concentrations of itraconazole ensure maximal CYP3A4 inhibition. Participants will be kept in the clinical unit under continuous medical supervision and monitoring for 3 days after single administration of RO7017773 alone and one week after RO7017773 administration in combination with itraconazole. They will remain in the clinical unit up to 3 days after the administration of the last dose of itraconazole.

More detailed information about the known and expected benefits in the context of potential risks and reasonably expected AEs of RO7017773 and itraconazole are provided in the [Investigator's Brochure](#) and in the [SmPC](#), respectively.

3. OBJECTIVES AND ENDPOINTS

The objectives and corresponding endpoints are provided in [Table 4](#).

Table 4 Objectives and Endpoints

Objectives	Endpoints
Primary	

To investigate the effect of multiple oral doses of itraconazole on the pharmacokinetics (PK) of a single oral dose of RO7017773 in healthy participants.	
RO7017773 concentrations and RO7017773 PK parameters.
Secondary	

To assess the safety and tolerability of a single oral dose of RO7017773 alone and in combination with multiple doses of itraconazole in healthy participants.	
Incidence and severity of AEs.Changes in vital signs, physical findings, ECG parameters, and clinical laboratory results during and after RO7017773 administration alone and in combination with itraconazole.Change in suicide risk (using the Columbia Suicide Severity Rating Scale [C-SSRS]).

To assess the PK of itraconazole following multiple oral doses of itraconazole alone and in combination with a single oral dose of RO7017773 to ensure adequate CYP3A4 inhibition.	
Concentrations and PK parameters for itraconazole and its metabolites.
Exploratory	

To screen for the presence of RO7017773-derived metabolites.To assess the relative abundance and PK parameters of any metabolite as appropriate.To investigate whether genetic variants of drug-metabolizing enzymes (e.g. CYP3A4) can be related to the pharmacokinetic behavior or observations on the safety of RO7017773 in combination with itraconazole.	
PK concentrations of RO7017773-derived metabolites, if appropriate.PK parameters of RO7017773-derived metabolites, if appropriate.Clinical genotyping.

4. **STUDY DESIGN**

4.1 **OVERALL DESIGN**

An overview of the study design is provided in Section [1.2](#).

This is a single-center, non-randomized, open-label, one-sequence, two-period crossover study in healthy male and female participants to investigate the effect of CYP3A inhibition on the PK of RO7017773 using concomitant administration of itraconazole as CYP3A inhibitor.

In Period 1, participants will be administered a single oral dose of RO7017773 alone in fed state. In Period 2, after a wash-out period of 10 days, participants will receive multiple doses of itraconazole in fed state for 9 days and be administered [REDACTED] RO7017773 [REDACTED] in combination with itraconazole [REDACTED].

Healthy participants will be admitted to the clinical unit on Day -1 of Period 1. An oral dose of [REDACTED] RO7017773 will be administered alone, 30 minutes after starting a standardized breakfast on the morning of Day 1 of Period 1. Participants will be discharged on the morning of Day 4 after all assessments have been completed. They will return to the clinical unit for 3 ambulatory visits at Day 5, Day 6, and Day 8 for PK sampling and safety monitoring.

After a wash-out period of 10 days, participants will be admitted to the clinical unit on Day -1 of Period 2 and will remain in-house until the morning of Day 12. They will be administered 200 mg of itraconazole BID (12 hours apart) *on Day 1 and 200 mg of itraconazole QD from Day 2 to Day 9* in Period 2. Itraconazole will be administered as oral capsules containing 200 mg every 12 hours (BID), 30 minutes after starting a standardized breakfast in the morning and after a standardized dinner in the evening *on Day 1 only and on Days 2 to 9 oral capsules containing 200 mg once a day (QD), 30 minutes after starting a standardized breakfast in the morning*. On the morning [REDACTED]

[REDACTED] RO7017773 will be administered to each participant in combination with the morning dose of itraconazole. Participants will be discharged on the morning of Day 12 after all assessments have been completed. They will return to the clinical unit for 4 ambulatory visits at Day 13, Day 14, Day 15, and Day 16 for PK sampling and safety monitoring.

Participants will visit the clinical research unit for a safety follow-up visit 15 to 20 days after the last dose of itraconazole.

[REDACTED] Similarly, safety data will be collected in Period 1 and Period 2 in order to assess the effect of itraconazole on the safety profile of RO7017773.

4.1.1 Length of the Study

The total duration of the study for each participant will be up to 10 weeks, divided as follows (see also Section 1.3, Figure 1):

- **Screening:** Up to 4 weeks
- **In-clinic and dosing Period 1:** Day -1 to Day 4 with a single oral dose of [REDACTED] RO7017773 administered on Day 1.
- **Ambulatory visit Period 1:** Day 5, 6 and 8 (PK sampling and safety monitoring)
- **Washout Period:** Approximately 9 days *to a maximum of 18 days (± 1 Day)* (i.e., between Day 1 of Period 1 and Day -1 of Period 2).
- **In-clinic and dosing Period 2:** Day -1 to Day 12 with multiple oral dose administrations of itraconazole (200 mg BID *Day 1 and 200 mg QD Days 2 to Day 9*) from Day 1 to Day 9 and co-administration of [REDACTED] RO7017773 with itraconazole on the morning [REDACTED].
- **Ambulatory visit Period 2:** Day 13, Day 14, Day 15, and Day 16 (PK sampling and safety monitoring).
- **Follow-up visit:** 15 to 20 days after the last dose of itraconazole.

4.2 STOPPING RULES CRITERIA

4.2.1 Study Stopping Criteria

Dosing will be stopped at any time during the study if one of the following circumstances occurs in the participants, unless it is determined by the Investigator that the occurrence is not related to the administration of study drug:

- One serious adverse event
- Severe non-serious adverse events (i.e., considered at least related to RO7017773 administration) in two or more participants

4.2.2 Individual Stopping Criteria

Dosing will be stopped at any time during the study in a given individual participant if compared to baseline one of the following circumstances occurs, unless it is determined by the Investigator that the occurrence is not related to the administration of the study drug:

- a serious adverse event
- one (or more) severe adverse events (see section 3.1 of Appendix 2 for definition of severity)
- clinically significant changes in vital signs or ECG, such as a QTcF > 480 ms (if confirmed by repeated measurement within 30 minutes) or QTcF change-from-baseline > 60 ms (if confirmed by repeated measurement within 30 minutes)
- an elevation of ALT > 3 x ULN, with an associated increase in bilirubin > 2 x ULN and with ALP > 2 ULN, in the absence of an alternative explanation
- other findings, that at the joint discretion of the Sponsor Clinical Pharmacologist, the Sponsor Safety Science leader and the Investigator, indicate that dosing in this individual should be stopped

- [REDACTED]

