7.1 DISCONTINUATION OF STUDY TREATMENT

See the SoA (Section [1.3](#)) for data to be collected at the time of treatment discontinuation and follow-up and for any further evaluations that need to be completed.

Discontinuation of study intervention for abnormal liver function should be considered by the Investigator when a participant meets one of the conditions outlined (Section [6](#), [Appendix 3](#)) or if the Investigator believes that it is in best interest of the participant.

Participants who discontinue study treatment prematurely will be asked to return to the clinic for a study completion/early termination visit (see Section [8.10.3](#)) and may undergo follow-up assessments (see Section [8.10.4](#)). The primary reason for premature study treatment discontinuation should be documented on the appropriate eCRF.

Participants who discontinue study treatment prematurely may be replaced in order to ensure obtaining 12 evaluable participants.

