8.3.6 Non-Serious Adverse Events of Special Interest

NSAESIs are required to be reported by the Investigator to the Sponsor immediately (i.e., no more than 24 hours after learning of the event; see [Appendix 2](#) for reporting instructions).

NSAESIs for this study include the following:

- Cases of an elevated ALT or aspartate aminotransferase (AST) in combination with either an elevated bilirubin or clinical jaundice, as defined in [Appendix 3](#).
- Suspected transmission of an infectious agent by the study treatment, as defined below:

Any organism, virus, or infectious particle (e.g., prion protein transmitting transmissible spongiform encephalopathy), pathogenic or non-pathogenic, is considered an infectious agent. A transmission of an infectious agent may be suspected from clinical symptoms or laboratory findings that indicate an infection in a

patient exposed to a medicinal product. This term applies only when a contamination of the study treatment is suspected.

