3.1. ASSESSMENT OF SEVERITY

The Investigator will make an assessment of severity for each AE and SAE reported during the study and assign it to one of the categories provided in [Table 1](#) (as a guidance for assessing adverse event severity).

The terms "severe" and "serious" are not synonymous. Severity refers to the intensity of an adverse event (rated as mild, moderate, or severe, or according to a pre-defined grading criteria [e.g., National Cancer Institute Common Terminology Criteria for Adverse Events [NCI CTCAE] criteria]; the event itself may be of relatively minor medical significance (such as severe headache without any further findings).

Severity and seriousness need to be independently assessed for each adverse event recorded on the eCRF.

Serious adverse events are required to be reported by the Investigator to the Sponsor immediately (i.e., no more than 24 hours after learning of the event).

Table 1 Adverse Event Severity Grading Scale

Severity	Description
Mild	Discomfort noticed, but no disruption of normal daily activity
Moderate	Discomfort sufficient to reduce or affect normal daily activity
Severe	Incapacitating with inability to work or to perform normal daily activity

Note: Regardless of severity, some events may also meet seriousness criteria. Refer to definition of a serious adverse event (see above).

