6. ABNORMAL LIVER FUNCTION TESTS

The finding of an elevated ALT or AST ($>3 \times \text{ULN}$) in combination with either an elevated total bilirubin ($>2 \times \text{ULN}$) or clinical jaundice in the absence of cholestasis or other causes of hyperbilirubinemia is considered to be an indicator of severe liver injury. Therefore, Investigators must report as an adverse event the occurrence of either of the following:

- Treatment-emergent ALT or AST $> 3 \times \text{ULN}$ in combination with total bilirubin $> 2 \times \text{ULN}$.
- Treatment-emergent ALT or AST $> 3 \times \text{ULN}$ in combination with clinical jaundice.

The most appropriate diagnosis or (if a diagnosis cannot be established) the abnormal laboratory values should be recorded on the Adverse Event eCRF (see [Appendix 2](#), Section [5.1](#)) and reported to the Sponsor immediately (i.e., no more than 24 hours after learning of the event), either as a serious adverse event or a non-serious adverse event of special interest (see Section [8.3.6](#)).

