9. HOSPITALIZATION OR PROLONGED HOSPITALIZATION

Any adverse event that results in hospitalization or prolonged hospitalization should be documented and reported as a serious adverse event (per the definition of serious adverse event in [Appendix 2](#)), except as outlined below.

An event that leads to hospitalization under the following circumstances should not be reported as an adverse event or a serious adverse event:

- Hospitalization for respite care
- Planned hospitalization required by the protocol (e.g., for study treatment administration or insertion of access device for study treatment administration)

- Hospitalization for a preexisting condition, provided that all of the following criteria are met:
 - The hospitalization was planned prior to the study or was scheduled during the study when elective surgery became necessary because of the expected normal progression of the disease.
 - The participant has not suffered an adverse event.

An event that leads to hospitalization under the following circumstances is not considered to be a serious adverse event, but should be reported as an adverse event instead:

- Hospitalization for an adverse event that would ordinarily have been treated in an outpatient setting had an outpatient clinic been available.

Appendix 4

Clinical Laboratory Tests

The tests detailed in [Table 1](#) will be performed by the local or central laboratory.

Protocol-specific requirements for inclusion or exclusion of participants are detailed in Sections [5.1](#) and [5.2](#), respectively, of the protocol.

Additional repeat or unscheduled tests may be performed at any time during the study as determined for necessary safety reasons or technical issues with the samples.

Table 1 Protocol-Required Safety Laboratory Assessments

Laboratory Assessments	Parameters
Hematology	
Leucocytes, erythrocytes, hemoglobin, hematocrit, platelets, differential count (neutrophils, eosinophils, basophils, monocytes, lymphocytes, other cells).
Clinical Chemistry	
Sodium, potassium, chloride, bicarbonate, glucose (fasting), urea, creatinine, protein, albumin, phosphate, calcium, total and direct bilirubin, alkaline phosphatase, ALT, AST, urate, LDH.
Coagulation	
Prothrombin time (INR) and activated thromboplastin time (aPTT).

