11.2. Clinical laboratory data

The following clinical laboratory parameters will be measured (see section 14.1):

- at screening visit,
- in Period 1: on Day -1, Day 3 and Day 8,
- in Period 2: on Day -1, Day 4, Day 7, Day 10 and Day 16,
- at follow-up visit.

Haematology parameters will be listed and grouped as follows:

- Red blood cells: erythrocytes ($10^{12}/L$), hematocrit (ratio) and hemoglobin (g/L).
- White blood cells: basophils ($10^9/L$), eosinophils ($10^9/L$), leukocytes ($10^9/L$), lymphocytes ($10^9/L$), monocytes ($10^9/L$) and neutrophils ($10^9/L$).
- Other parameters: platelets ($10^9/L$).

Blood chemistry parameters will be listed and grouped as follows:

- Liver function: alanine aminotransferase (IU/L), alkaline phosphatase (IU/L), aspartate aminotransferase (IU/L), bilirubin ($\mu\text{mol}/L$), direct bilirubin ($\mu\text{mol}/L$).
- Renal chemistry: creatinine ($\mu\text{mol}/L$) and urea (mmol/L).
- Electrolytes: bicarbonate (mmol/L), calcium (mmol/L), chloride (mmol/L), phosphate (mmol/L), potassium (mmol/L) and sodium (mmol/L).
- Metabolism parameters: cholesterol (mmol/L), glucose (mmol/L), lactate dehydrogenase (IU/L), triglycerides (mmol/L) and urate ($\mu\text{mol}/L$).
- Other proteins: albumin (g/L) and protein (g/L).

Urinalysis parameters will be listed and grouped as follows:

- Planned urinalysis parameters: dipstick determination of erythrocytes, glucose, leukocytes, nitrite and protein, pH and specific gravity.

- Direct microscopy (in case of abnormal urinalysis parameters and in the listing only): cytology (erythrocytes, leukocytes, epithelial cells, granular casts and hyaline casts), bacteria (/uL) and crystals (calcium phosphate crystals, calcium oxalate crystals and monosodium urate crystals).

For haematology and blood chemistry, raw data and changes from baseline will be described by treatment group and measurement time.

For urinalysis, raw data (planned parameters) will be described by summary statistics or frequency tables by treatment group and measurement time.

For haematology, blood chemistry and urinalysis, values higher or lower than the laboratory reference range (H, L) will be listed.

Values (raw data and changes from baseline) will be listed and data out of normal ranges will be flagged with clinical significance information.

Urinalysis values will be listed, including direct microscopy, if any.

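### The liver stopping criterion in Protocol 4.2.2 also requires raised ALP and leaves out AST and jaundice, so it misses the non-cholestatic pattern that Appendix 3 treats as a sign of severe liver injury

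*Protocol*

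**What the plan says.** Protocol 4.2.2 (Individual Stopping Criteria) has one visible liver-specific bullet: "an elevation of ALT > 3 x ULN, with an associated increase in bilirubin > 2 x ULN and with ALP > 2 ULN", provided there is no alternative explanation. AST and jaundice are not mentioned.

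Appendix 3, Section 6 (Abnormal Liver Function Tests) takes ALT or AST above 3 x ULN, with either total bilirubin above 2 x ULN "or clinical jaundice in the absence of cholestasis or other causes of hyperbilirubinemia is considered to be an indicator of severe liver injury". Its two reporting bullets use the same transaminase and bilirubin limits, or jaundice, without reference to ALP. Such a case goes to the sponsor within 24 hours, "either as a serious adverse event or a non-serious adverse event of special interest". Section 8.3.6 lists the same event type: "Cases of an elevated ALT or aspartate aminotransferase (AST) in combination with either an elevated bilirubin or clinical jaundice".

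Section 7.1 links the Appendix 3 conditions to treatment: "Discontinuation of study intervention for abnormal liver function should be considered by the Investigator when a participant meets one of the conditions outlined". Section 4.2.2 also stops dosing for a serious adverse event, for a severe adverse event, and for other findings at the joint discretion of two sponsor roles and the investigator. Appendix 2, Section 3.1 defines severe as "Incapacitating with inability to work or to perform normal daily activity".

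**The concern.** The stopping criterion and the definition of severe liver injury point in different directions. Appendix 3 is concerned with injury without cholestasis. The 4.2.2 bullet applies only when ALP is also raised, so a participant with marked ALT and bilirubin elevation and normal ALP does not meet it. Nor does a participant whose transaminase rise is in AST alone, or one with jaundice but bilirubin not above 2 x ULN.

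The participants are healthy volunteers. Section 2.2.2 says itraconazole has been associated with rare serious hepatotoxicity, in some cases without pre-existing liver disease and in some cases within the first week of treatment. Dosing in Period 2 runs from Day 1 to Day 9. In the cases that the bullet misses, whether dosing continues depends on how the event is classified or on discretion.

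**Working it through.** The protocol gives no figure to reproduce here. The check compares the two rules over every combination of five yes/no conditions: ALT > 3 x ULN, AST > 3 x ULN, bilirubin > 2 x ULN, jaundice, and ALP > 2 x ULN. That gives 2^5 = 32 patterns.

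**Rules**

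- Appendix 3 reporting: (ALT or AST) and (bilirubin or jaundice), ALP free. Count: 3 x 3 x 2 = 18.
- 4.2.2 stop: ALT and bilirubin and ALP, with AST and jaundice free. Count: 2 x 2 = 4, all inside the 18.
- Reported but not meeting the stop: 18 - 4 = 14.

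**The 14 patterns**

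| Pattern | Count |
|---|---|
| ALT and bilirubin raised, ALP not > 2 x ULN | 2 x 2 = 4 |
| AST raised, ALT not > 3 x ULN | 3 x 2 = 6 |
| ALT raised with jaundice, bilirubin not > 2 x ULN | 2 x 2 = 4 |

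**Split by ALP**

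- ALP not above 2 x ULN: the stop applies in 0 of 9 reportable patterns.
- ALP above 2 x ULN: it applies in 4 of 9.

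Example: ALT 10 x, bilirubin 4 x and ALP 1 x ULN must be reported under Appendix 3 but does not meet the 4.2.2 bullet.

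**Effect of two possible edits**

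- Delete only the ALP condition: 2 x 2 x 2 = 8 of 18 covered.
- Adopt the full Appendix 3 combination: 18 of 18 covered, before the exceptions for an alternative explanation or an unrelated event.

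**Doses at stake.** Itraconazole: 2 on Day 1 plus 8 on Days 2 to 9 = 10. SAP 11.2 schedules safety laboratory tests "in Period 2: on Day -1, Day 4, Day 7, Day 10 and Day 16", so Day 4 and Day 7 are the draws that fall during dosing.

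| Draw | Doses already given | Avoidable if result known before that day's dose | Avoidable if known after it |
|---|---|---|---|
| Day 4 | 2 + 2 = 4 | 10 - 4 = 6 | 5 |
| Day 7 | 2 + 5 = 7 | 10 - 7 = 3 | 2 |

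SAP 11.2 also has draws on Period 1 Day 3 and Day 8. An abnormal result there would come before any itraconazole dose.

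**Other visible routes to a stop**

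- Section 7.1 refers to the Appendix 3 conditions but only asks the investigator to consider stopping.
- The serious-event route (4.2.1 and 4.2.2) needs the case to be classed as serious, and Appendix 3 allows it to be reported as non-serious.
- The severe-event route needs incapacity, which a laboratory finding need not cause.
- The joint-discretion bullet, and the discussion of safety concerns with the sponsor in Section 8, are discretionary by their terms.

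**The case against.** The strongest reply is that such a participant would very probably be stopped anyway.

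- Section 2.2.2 says itraconazole should be discontinued if clinical signs of liver disease develop. Jaundice is such a sign, and 10 of the 14 uncovered patterns include it (2 + 4 + 4).
- Appendix 2, Section 2 says important medical events that may jeopardise the participant should usually be classed as serious. That would trigger the individual stop, and the study stop in 4.2.1 unless the event was judged unrelated.
- Section 7.1 already brings all 18 patterns to the investigator's attention, and a reporting threshold wider than an automatic stop is not in itself a contradiction.
- Every 4.2.2 criterion yields to a judgement that the event is unrelated, so even an amended rule would not be fully automatic.
- Five of the 14 patterns have ALP above 2 x ULN, so they are not the non-cholestatic pattern if ALP is taken as the marker.
- Part of the list in 4.2.2 is redacted.

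Much of this stands as context. A competent investigator would probably stop dosing, and in-house supervision, 24-hour reporting and the entry limit of 1.5 x ULN for ALT and bilirubin lower the risk. The pattern counts show where the rules differ and say nothing about risk.

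It does not close the gap. The text in 2.2.2 is background and does not reach the 4 patterns without jaundice. The presumption of seriousness is still a judgement, and Appendix 3 expressly permits the non-serious class. The exceptions in 4.2.2 need a positive finding before dosing continues, whereas 7.1 needs a positive decision before it stops.

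**Conclusion.** The concern holds. As written, the only visible liver-specific mandatory stop is narrower than the protocol's own description of severe liver injury. It covers 4 of the 18 reportable patterns, and none of the 9 in which ALP is not above 2 x ULN. No other visible provision assures a stop in the remaining cases. The number of itraconazole doses affected is at most 6 of 10 from a Day 4 result and 3 of 10 from a Day 7 result, counting scheduled Period 2 draws only.

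The conclusion rests on the wording of the bullet. It does not depend on any ALP cut-off for cholestasis, which the protocol does not give. It is limited to visible text: if the redacted bullet in 4.2.2 already covers these cases, what remains is an inconsistency with Appendix 3 and not a gap in protection. The point should be fixed, because it concerns the safety of healthy volunteers and the correction is cheap.

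**What to change.** In 4.2.2, replace the liver bullet with: *ALT or AST above 3 x ULN together with total bilirubin above 2 x ULN or clinical jaundice, with no alternative explanation.* This drops the ALP condition and adds AST and jaundice. Deleting the ALP condition alone is not enough, since it reaches only 8 of the 18 patterns.

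In 7.1, state that dosing will be stopped when this criterion is met, and keep the softer wording for other liver abnormalities only. The existing exceptions for an alternative explanation and for unrelated events stay in place, so a benign cause need not force a stop.

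The cost is a protocol amendment to two sections. No new tests are needed, because the Appendix 4 chemistry panel already includes "total and direct bilirubin, alkaline phosphatase, ALT, AST, urate, LDH". The downside is possibly a rare additional participant stopped. Enrolment of 14 to 18 for 12 evaluable leaves 14 - 12 = 2 to 18 - 12 = 6 spare.
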